7.3 Patient Reported Outcomes (Quality of life assessment)

Quality of life (QOL) will be measured using the EPIC-26 instrument according to the time points delineated in the Time and Events Table (Section 8.1).³⁷ Expanded Prostate Cancer Index Composite (EPIC-26) is a validated prostate cancer-specific health-related QOL (HRQOL) instrument that measures urinary, bowel, sexual, and hormonal symptoms related to prostate cancer treatments, including prostatectomy, radiotherapy, and hormonal therapy. Summary and subscale scores were derived by content and factor analyses. Test-retest reliability and internal consistency were high for EPIC urinary, bowel, sexual, and hormonal domain summary scores (each $r \ge 0.80$ and Cronbach's alpha ≥ 0.82) and for most domain-specific subscales. Correlations between function and bother subscales within domains were high (r > 0.60). Correlations between different primary domains were consistently lower, indicating that these domains assess distinct HRQOL components.

Another scoring protocol to assess the quality of life is the Prostate Cancer Symptom Indices (PCSI). This assessment will be performed per timing described in the Time and Events Table (Section 8.1). The PCSI has 4 domains: urinary obstruction and irritation (5 items), urinary incontinence (3 items), sexual dysfunction (5 items), and bowel problems (6 items). Each domain is scored from

CONFIDENTIAL UNIVERSITY OF NORTH CAROLINA July 24, 2024

0 to 100, with a higher score indicating more or worse dysfunction. Minimal clinically important differences for PCSI domains have not been defined. Parallel to each of the 4 domains are additional questions that ask patients about the magnitude of bother related to urinary obstruction and irritation, urinary incontinence, sexual, and bowel symptoms. In addition to numerical scoring for each domain described above, the PCSI has established functional levels (normal, intermediate, and poor) that incorporate the symptom as well as bother questions. These function levels complement the score reporting because QOL score changes are well recognized to be difficult for patients and physicians to interpret. Normal function describes a patient with essentially no dysfunction or distress in a domain (eg, normal function in the urinary incontinence domain describes a man who has full urinary control without incontinence). Intermediate function describes a patient with at least 1 distressful symptom but none very distressful (e.g., intermediate urinary incontinence represents leaking only at certain times, and no more than a few drops). Poor function describes patients with at least 1 very distressful symptom (eg, poor sexual function represents no erections capable of intercourse or a lot of difficulty getting and keeping an erection). This classification adds clinical meaning to numerical scores, and also allowed analysis of QOL outcomes stratified by each participant's baseline level. Effect sizes between functional levels of the PCSI are large.

8.0 EVALUATIONS AND ASSESSMENTS

8.1 Time and Events Table

Study Assessments	Pre- radiation ¹	Radiation Therapy	1, 3, 6, 9, 12 months post- radiation ^{1,3}	2-5 years post- radiation ^{1, 3}
Assessment, consultation	X			
Informed Consent	X			
History and PE ¹	X			X
Performance Status	X			X
Quality of Life ²	X		X	X
Toxicity Evaluations ³	X		X	X ³
PSA Measurements	X		X	X
PSMA-PET/MRI+CT ⁴	X			
CBC, coagulations ⁵ , CMP	X			
Fiducials ⁶		Х		
Radiation planning ⁷		Х		
Androgen deprivation therapy ⁸		Х		
Radiation Therapy ⁹		Х		
Biopsy ¹⁰		Х		

Footnotes to Time and Events Table

- History and physical exam may be performed within 8 weeks prior to day 1 of study treatment. Other evaluations must be performed within 8 weeks priors to Day 1 (D1) of study treatment. Screening labs performed within 8 weeks prior to D1 of study treatment do not need to be repeated on D1. A window of +/- 30 days applies to all study visits unless otherwise specified.
- 2. EPIC-26 (A.4 Quality of Life according to EPIC-26) and PCSI (A.5 The local Quality of Life questionnaire)
- 3. Subject will be regularly followed and seen by the treating physician every 6 months for up to 5 years after treatment. Patients who have an ongoing ≥grade 2 or serious AE (SAE) will continue to be followed until the event is resolved or deemed irreversible by the investigator.
- 4. PSMA-PET/MRI+CT should be no later than the day of starting ADT.
- 5. INR or PT and PTT
- 6. During CK-SBRT, the subject will have MRI-compatible fiducials (e.g. gold) placed into the prostate by the radiation oncologist. These will be used for image guided radiation therapy.
- 7. The irradiation technique will be a combination of EBRT and BT. The highest planning priority will be to satisfy the restrictions of the bowel, rectum and bladder. Refer to Section 6.1.1.3 for additional details including dose on target volumes and planning priorities.
- 8. Androgen deprivation therapy will start no earlier than the same day of the PSMA-PET/CT scan. Duration per standard of care.
- 9. Radiation therapy will consist of:
 - a. 5 weeks of external beam radiation (EBRT). Typically 8 weeks after initiation of ADT.
 - i. Prostate +/- pelvic LNs (determined by radiographic findings): 1.8 Gy/fx x 25fx
 - ii. Regional radiographically pos LNs: 2.25 Gy/fx x 25 fx
 - b. SBRT with CyberKnife
 - i. DIL: 8.0 Gy/fx x 3fx.
- 10. At time of fiducial markers placement, prostate GTVs (i.e. DILs) will be biopsied. Refer to Section 7.2.3 for additional details.

8.2 **Pre-Study Assessments**

Patients will undergo the standard UNC work up for patients diagnosed with unfavorable intermediate/high-risk prostate cancer. They will undergo the standard pre-treatment evaluations for external beam radiotherapy and SBRT and androgen deprivation therapy. Their care will not deviate from any other patient that comes through the multi-disciplinary clinic.

8.3 Treatment Assessments

Patients will undergo the standard UNC treatment assessment for patients with unfavorable intermediate/high-risk prostate cancer under treatment. They will undergo the treatment assessments for external beam radiotherapy and SBRT and androgen deprivation therapy. Their care will not deviate from any other patient that comes through the radiation oncology clinic.

8.4 Post-Treatment/Follow-up Assessments

Subjects will be followed for five years after radiation therapy, with a final study follow-up visit at 5 years after the end of treatment. Subjects who have an ongoing \geq grade 2 or serious AE (SAE) will continue to be followed until the event is resolved or deemed irreversible by the investigator.

8.5 Early Termination Visit

Subjects may withdraw voluntarily from participation in the study at any time. Subjects may also withdraw voluntarily from receiving the study intervention for any reason. No specific evaluations will be required in the setting of early termination.

8.6 Assessment of Safety

All patients who received treatment (i.e. radiation) will be evaluated for toxicity at specified time points throughout the study; toxicity will be measured according to CTCAE version 5.0.

8.7 Assessment of Efficacy

Patients will be followed with routine PSA tests at follow up visits, as is standard practice.

8.7.1 Other Efficacy Parameters

Biochemical control after radiation is measured by PSA and defined by the Phoenix criteria.³³

9.0 ADVERSE EVENTS

9.1 **Definitions**

9.1.1 Adverse Event (AE)

An adverse event (AE) is any untoward medical occurrence (e.g., an abnormal laboratory finding, symptom, or disease temporally associated with the use of a drug) in a patient or clinical investigation subject administered a pharmaceutical product and which does not necessarily have a causal relationship with this treatment. An AE can therefore be any unfavorable and unintended sign (including an abnormal laboratory finding), symptom, or disease temporally associated with the use of a medicinal product, whether or not related to the medicinal product.

Hospitalization for elective surgery or routine clinical procedures that are not the result of an AE (e.g., surgical insertion of central line) need not be considered AEs and should not be recorded as an AE. Disease progression should not be recorded as an AE, unless it is attributable by the investigator to the study therapy.

9.1.2 Suspected Adverse Reaction (SAR)

A suspected adverse reaction (SAR) is any AE for which there is a *reasonable possibility* that the drug is the cause. *Reasonable possibility* means that there is evidence to suggest a causal relationship between the drug and the AE. A suspected adverse reaction implies a lesser degree of certainty about causality than adverse reaction, which means any adverse event caused by a drug.

Causality assessment to a study drug is a medical judgment made in consideration of the following factors: temporal relationship of the AE to study drug exposure, known mechanism of action or side effect profile of study treatment, other recent or concomitant drug exposures, normal clinical course of the disease under investigation, and any other underlying or concurrent medical conditions. Other factors to consider in considering drug as the cause of the AE:

- Single occurrence of an uncommon event known to be strongly associated with drug exposure (e.g., angioedema, hepatic injury, Stevens-Johnson Syndrome)
- One or more occurrences of an event not commonly associated with drug exposure, but otherwise uncommon in the population (e.g., tendon rupture); often more than once occurrence from one or multiple studies would be needed before the sponsor could determine that there is *reasonable possibility* that the drug caused the event.
- An aggregate analysis of specific events observed in a clinical trial that indicates the events occur more frequently in the drug treatment group than in a concurrent or historical control group

9.1.3 Unexpected AE or SAR

An AE or SAR is considered unexpected if the specificity or severity of it is not consistent with the applicable product information (e.g., Investigator's Brochure

(IB) for an unapproved investigational product or package insert/summary of product characteristics for an approved product). Unexpected also refers to AEs or SARs that are mentioned in the IB as occurring with a class of drugs or as anticipated from the pharmacological properties of the drug but are not specifically mentioned as occurring with the particular drug under investigation.

9.1.4 Serious AE or SAR

An AE or SAR is considered serious if, in the view of either the investigator or sponsor, it results in any of the following outcomes:

- Death;
- Is life-threatening (places the subject at immediate risk of death from the event as it occurred);
- Requires inpatient hospitalization (>24 hours) or prolongation of existing hospitalization;*
- Results in congenital anomaly/birth defect;
- Results in a persistent or significant incapacity or substantial disruption of the ability to conduct normal life functions;
- Important medical events that may not result in death, be lifethreatening, or require hospitalization may be considered a serious adverse drug experience when, based upon appropriate medical judgment, they may jeopardize the patient or subject and may require medical or surgical intervention to prevent one of the outcomes listed in the definition. For reporting purposes, also consider the occurrences of pregnancy as an event which must be reported as an important medical event.

*Hospitalization for anticipated or protocol specified procedures such as administration of chemotherapy, central line insertion, metastasis interventional therapy, resection of primary tumor, or elective surgery, will not be considered serious adverse events.

9.2 Documentation of non-serious AEs or SARs

For non-serious AEs or SARs, documentation must begin from day 1 of study treatment (i.e. radiation) and continue through the 5-year follow-up period after treatment is discontinued.

Collected information should be recorded in the Case Report Forms (CRF) for that patient. Please include a description of the event, its severity or toxicity grade, onset and resolved dates (if applicable), and the relationship to the study drug. Documentation should occur at least monthly.

9.3 SAEs or Serious SARs

9.3.1 Timing

After informed consent but prior to initiation of study medications, only SAEs caused by a protocol-mandated intervention will be collected (e.g. SAEs related to invasive procedures such as biopsies, medication washout.

For any other experience or condition that meets the definition of an SAE or a serious SAR, recording of the event must begin from day 1 of study treatment (i.e. radiation) and continue through the 5 year follow-up period after treatment is discontinued.

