7.1.4 Adverse Events

Events should be assessed per NCI-CTCAE criteria 5.0. Information regarding occurrence of adverse events will be captured throughout the study. Duration (start and stop dates), severity/grade, outcome, treatment and relation to study treatment will be recorded in the case report form. A dose-limiting toxicity is defined as all Grade 3 or above acute toxicities attributed to the treatment under study. The accrual will be halted if the number of patients with dose-limiting toxicities equals to or exceeds a rate of 30%.

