7.2.3 Pathology

At time of fiducial markers placement, GTVs (i.e. DILs) will be biopsied by the treating radiation oncologist and a urologist. Two cores will be taken per GTV and placed in buffered formalin containers. This is a research only biopsy and will be used to evaluate the sensitivity and specificity of PSMA-PET/MRI vs PSMA-PET/CT. It will not require any additional visits or cost for the subject. These samples will be collected and accessioned with coded identifiers by the Tissue Procurement Facility (TPF). Specimen processing, embedding and histologic sectioning will be performed by the Translational Pathology Laboratory (TPL) and slides interpreted by the collaborating pathologist.

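### Non-serious AE recording starts at radiation day 1, so earlier harms of the study's own procedures need not be documented, and the pre-radiation SAE rule ends at an undefined point

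*Combined protocol and SAP*

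**What the plan says.** - **Non-serious events (9.2):** "For non-serious AEs or SARs, documentation must begin from day 1 of study treatment (i.e. radiation"; recording then continues through the 5-year follow-up. Onset and resolution dates are recorded, with the relationship to the study drug.
- **Serious events before treatment (9.3.1):** "After informed consent but prior to initiation of study medications, only SAEs caused by a protocol-mandated intervention will be collected", with biopsies named as an example. The rule ends when study medications start.
- **All other serious events (9.3.1):** "recording of the event must begin from day 1 of study treatment (i.e. radiation".
- **General statement (7.1.4):** "Information regarding occurrence of adverse events will be captured throughout the study". Start and stop dates and the relation to study treatment go on the CRF.
- **Research biopsy (7.2.3):** taken when the fiducials are placed. "This is a research only biopsy and will be used to evaluate the sensitivity and specificity of PSMA-PET/MRI vs PSMA-PET/CT"
- **Timing:** 6.1.1.1.1 puts the scan 1-2 weeks after fiducial placement and ADT on the scan day or later. Footnote 9a of the Time and Events Table (8.1) times external beam radiation: "Typically 8 weeks after initiation of ADT".
- **Pre-radiation check (8.1):** a toxicity evaluation is marked in the pre-radiation column.

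**The concern.** The trial exposes men to a tracer injection, MRI contrast and a biopsy done only for research, with fiducials placed at the same time. If these happen before radiation, the non-serious AE rule is not yet running. Non-serious does not mean mild. In Appendix A.3, urinary retention needing a catheter is grade 2 and gross haematuria appears under grade 3. Either can fail to meet a seriousness criterion in 9.1.4, where hospitalization counts only beyond 24 hours. The safety record would then be incomplete for procedures that the study itself requires. Sections 7.1.4 and 9.2 also give study staff opposite instructions, so two coordinators could record the same event differently.

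**Working it through.** The plan states no figure on this point. The check adds up its intervals and sets its rules against them.

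**Inputs**
- Fiducials to scan: 1-2 weeks (6.1.1.1.1).
- Scan to ADT: 0 weeks or more (6.1.1.1.1; 8.1 footnotes 4 and 8).
- ADT to external beam radiation: typically 8 weeks (8.1 footnote 9a).
- External beam start to SBRT: roughly 6 weeks (6.1.1.1.3).
- Biopsy: at fiducial placement (7.2.3; 8.1 footnote 10).

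**Time from each procedure to radiation day 1**
- Tracer and contrast: 0 + 8 = about 8 weeks before, longer if ADT starts after the scan day.
- Fiducials and biopsy on the 6.1.1.1.1 sequence: 1 + 8 = 9 to 2 + 8 = 10 weeks before.
- Fiducials and biopsy on 8.1 footnote 6, which places fiducials during CyberKnife treatment: about 6 weeks after radiation day 1.

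**Which recording rule applies**

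| Event | Before radiation day 1 | From radiation day 1 |
|---|---|---|
| Non-serious, any cause | None under 9.2; captured under 7.1.4 | 9.2 |
| Serious, caused by a protocol procedure | 9.3.1 first sentence, until study medications start | Recorded under 9.3.1 |
| Serious, other cause | Not collected | 9.3.1 second sentence |

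**Where the first SAE window ends.** Sections 9.2 and 9.3.1 equate study treatment with radiation, but nothing defines study medications.
- If the term means radiation, the two sentences meet and procedure-caused SAEs are covered throughout.
- If it means the tracer, contrast or ADT, the first window closes about 8 weeks before the second opens. Procedure-caused SAEs in between fall under neither sentence.

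**Biopsy timing.** The passages do not agree. Section 6.1.1.1.1 puts fiducials before the scan. Section 6.1.1.1.3 biopsies the GTVs, which are contoured from that scan. Section 7.2.3 ties the biopsy to fiducial placement. Footnote 6 of 8.1 puts fiducials during CyberKnife treatment. The Radiation Therapy column of 8.1 does not settle this, since it also holds ADT and planning, which precede radiation. At any time before radiation, non-serious biopsy harms are outside 9.2. At the footnote 6 time they are inside it, but arise alongside acute radiation effects. The tracer and contrast result does not depend on this conflict.

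**Attribution.** Section 9.2 asks for the relationship to study drug and 7.1.4 for the relation to study treatment. An entry of not related can say that radiation was not the cause, but neither field can name the biopsy, fiducials, tracer or contrast.

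**The case against.** The strongest reply is that the serious harms that matter most are already covered. Section 9.3.1 collects procedure-caused SAEs from consent and names biopsies. Its next sentence deals with any other event, so the natural reading is that the two windows meet at radiation day 1. Section 6.3 calls hormone therapy standard care, which weighs against ADT as a study medication. This largely stands: the SAE defect is an undefined term, not a demonstrated gap. A reader might infer that about 8 weeks per man have no SAE rule at all. That follows only on one reading of the term.

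A reader might also infer that biopsy events will be counted as radiation toxicity or DLTs. The documents do not show this. Onset dates are recorded, and the DLT definition in 6.4 requires attribution to the treatment under study, so a miscount needs an error of judgment.

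The pre-radiation toxicity evaluation helps too. It must fall within 8 weeks before day 1, so on typical intervals it would follow the scan. It is still one visit, not tied to any procedure. It does not require resolved events to be documented, and it does not move the start date in 9.2.

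Nor does the schedule defeat objective 3.2.1. That objective concerns target definition, and its endpoint in 4.2.1 is grade 3+ GU and GI toxicity during and after radiation. The image-adapted dose is itself delivered inside the collection window.

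Finally, restricting pre-radiation SAE collection to procedure-caused events is a deliberate and acceptable choice. It gives no reason to collect every unrelated event.

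**Conclusion.** The concern holds in a limited form and should be corrected.

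- **Established from the text:** non-serious harms of the tracer and contrast, about 8 weeks before radiation, need not be documented under 9.2. This contradicts 7.1.4.
- **Conditional on the 6.1.1.1.1 sequence:** the same applies to the fiducials and research biopsy, about 9-10 weeks before radiation. It does not apply if they occur during CyberKnife treatment.
- **Conditional on the meaning of study medications:** procedure-caused SAEs are either fully covered or uncovered from the tracer, contrast or ADT until radiation day 1.
- **Possible, not shown:** misattribution to radiation or to a DLT. No effect on the 12-month late-toxicity endpoint is shown.

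The intervals rest on the protocol's typical timings. The documents give no rate for procedure complications, so the number of events missed cannot be estimated from them.

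**What to change.** 1. In 9.3.1, end the pre-radiation SAE rule at day 1 of radiation, so that the two windows meet.
2. In 9.2 and 9.3.1, record adverse events of all grades related to a protocol procedure (biopsy or fiducials, tracer, contrast) from the first such procedure. Unrelated events can still start at radiation day 1.
3. Add those procedures as causality categories on the existing CRF, separate from radiation.
4. Align 7.1.4 with the revised windows.
5. Reconcile the fiducial and biopsy timing across 6.1.1.1.1, 6.1.1.1.3, 7.2.3 and footnotes 6 and 10 of 8.1.

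The cost is a few more AE entries and one CRF field. Amendment 6 supports early closure, so for men already enrolled the practical step is to state in the report which collection window was applied and how procedure-related events were attributed.

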9.3.2 Documentation and Notification

SAEs or Serious SARs must be recorded in the SAE console within Oncore[™] for that patient within 24 hours of learning of its occurrence. Additionally, the UNC Study Coordinator must also be notified via email of all SAEs within 24 hours of learning of its occurrence.

9.4 Adverse Event Reporting

9.4.1 IRB Reporting Requirements:

The UNC-IRB will be notified of all SAEs that qualify as an Unanticipated Problem as per the UNC IRB Policies using the IRB's web-based reporting system within 7 days of the Investigator becoming aware of the problem. Please note, these events must be reported to the sponsor within 24 hours of learning of the occurrence.

9.4.2 FDA Expedited Reporting requirements for studies conducted under an IND:

A sponsor must report any suspected adverse reaction that is both serious and unexpected to the FDA. The sponsor must report an adverse event as a suspected adverse reaction only if there is evidence to suggest a causal relationship between the drug and the adverse event. SARs are defined in Section 9.1.2.

The sponsor must submit each IND safety report on FDA Form 3500A. Each notification to FDA must bear prominent identification of its contents, i.e., "IND Safety Report," and must be transmitted to the review division that has the responsibility for review of the IND. In each IND safety report, the sponsor must identify all IND safety reports previously submitted to FDA concerning a similar suspected adverse reaction, and must analyze the significance of the suspected adverse relevant information.

Timing

FDA must be notified of potential serious risks within 15 calendar days after the sponsor determines the event requires reporting. FDA must be notified of

CONFIDENTIAL UNIVERSITY OF NORTH CAROLINA July 24, 2024

unexpected fatal or life-threatening suspected adverse reactions as soon as possible but in no case later than 7 calendar days after the sponsor's initial receipt of the information. The sponsor must be notified of the SAE by the investigator within 24 hours of the event. If the results of a sponsor's investigation show that an adverse event not initially determined to be reportable is reportable, the sponsor must report such suspected adverse reaction in an IND safety report as soon as possible, but in no case later than 15 calendar days after the determination is made.

Follow-up

The sponsor must promptly investigate all safety information it receives. Relevant follow-up information to an IND safety report must be submitted as soon as the information is available and must be identified as such, i.e., "Follow-up IND Safety Report." Additionally, upon request from FDA, the sponsor must submit to FDA any additional data or information that the agency deems necessary, as soon as possible, but in no case later than 15 calendar days after receiving the request.

Notification of Investigators

The sponsor must notify all participating investigators (i.e., all investigators to whom the sponsor is providing drug under its INDs or under any investigator's IND) in an IND safety report of potential serious risks, from clinical trials or any other source, as soon as possible, but in no case later than 15 calendar days after the sponsor determines that the information qualifies for reporting.

Process

If the sponsor deems that an event is both a serious adverse reaction (SAR) AND unexpected, it must also (in addition to Oncore) be recorded on the MedWatch Form 3500A as per 21 CFR 312.32. Unexpected adverse events or adverse reaction refers to an event or reaction that is not listed in the investigator's brochure or is not listed at the specificity or severity that has been observed; or if an investigator's brochure is not required or available, is not consistent with the risk information described in the general investigation plan or elsewhere in the current IND application.

The MedWatch 3500a form can be accessed at: http://www.fda.gov/Safety/MedWatch/HowToReport/DownloadForms/default.htm.

(Please be sure and access form 3500a, and not form 3500).

The MedWatch form should also be sent to the IND Specialist within 48 hours of the sponsor being aware of the event. The IND Specialist will submit the IND Safety Report via IND serial submission to the FDA review division.

All IND safety reports must be submitted on Form 3500A and be accompanied by Form 1571. The FDA must be notified or any unexpected or life-threatening suspected adverse reactions as soon as possible, but no later than 7 calendar days of learning of the event.

Additional Reporting Requirements

The following additional items must be reported via IND safety report:

- *Findings from other studies.* The sponsor must report any findings from epidemiological studies, pooled analysis of multiple studies, or clinical studies, whether or not conducted under an IND, and whether or not conducted by the sponsor, that suggest a significant risk to humans exposed to the drug.
- *Findings from animal or in vitro testing.* The sponsor must report any findings from animal or *in vitro* testing, whether or not conducted by the sponsor, that suggest a significant risk in humans exposed to the drug, such as reports of mutagenicity, teratogenicity, or carcinogenicity, or reports of significant organ toxicity t or near the expected human exposure.
- Increased rate of occurrence of serious suspected adverse reactions.

Additional Guidance

Please refer to 21CFR312.32 and "Guidance for Industry and Investigators: Safety Reporting Requirements for INDs and BA/BE Studies" for additional information and reporting requirements. All IND Safety Reports will be submitted in accordance with these regulations/guidances.

